10 STUDY OBJECTIVES AND ENDPOINTS

10.1 Study Objectives

Primary objective: To determine safety and tolerability of S 48168 (ARM210) treatment in *RYR1*-RM affected individuals.

Hypothesis: S 48168 (ARM210) treatment will have no safety concerns limiting further development and will be generally well tolerated in *RYR1*-RM patients.

Exploratory objectives:

1. To determine PK of a 28-day (not to exceed 30-day) administration of S 48168 (ARM210) in *RYR1*-RM affected individuals.

Hypothesis: There will be no clinically meaningful difference in S 48168 (ARM210) exposure at steady state in *RYR1*-RM affected individuals when compared to existing data established in healthy volunteers.

2. To explore if S 48168 (ARM210) treatment increases RyR1-calstabin1 binding in skeletal muscle of *RYR1*-RM affected individuals.

Hypothesis: S 48168 (ARM210) treatment will increase RyR1-calstabin1 binding, compared to baseline, as determined by co-immunoprecipitation of RyR1 and calstabin 1, and decrease relative Fluo-4 signal compared to baseline

3. To explore if S 48168 (ARM210) treatment improves muscle function, motor activity, and fatigue in *RYR1*-RM affected individuals.

Hypothesis: Treatment with S 48168 (ARM210) will increase hand grip, pinch, and quantitative muscle assessment strength, decrease the time to complete graded functional tests, increase the total MFM-32 % maximum score, and decrease the PROMIS-fatigue subscale score, when compared to baseline.

10.2 Study Endpoints

Primary endpoint:

Composite safety and tolerability profile

(Frequencies of the following: TEAEs \geq grade 2 in severity (CTCAE version 5), all SAEs, and all AESIs).

Exploratory Endpoints:

S 48168 (ARM210) pharmacokinetics

Day 1 composite PK profile (for study drug naïve participants only)

(Comprised of the following: AUC0-t, AUC0-inf, Cmax, Tmax, and t_{1/2}).

Day 28 (not to exceed Day 30) composite PK profile

(Comprised of the following: AU_{tau}, Cmax, Tmax, Cmin, RAAUC, and RACmax).

S 48168 (ARM210) pharmacodynamics

RyR1-calstabin1 binding

(Change from baseline in RyR1-calstabin1 binding (arbitrary units)).

RyR1 channel integrity

(Change from baseline in RyR1-mediated Ca²⁺ leak (arbitrary units)).

Muscle/motor function and fatigue

Hand grip strength (kg), pinch strength (kg).

Time taken to complete each of the following (seconds): walk 10-meters, supine to stand, ascend 4 stairs, and descend 4 stairs.

MFM-32 score for domains 1, 2, 3, and total (% of maximum score).

PROMIS-fatigue subscale score (t-score).

Quantitative muscle strength (kg)

11 INVESTIGATIONAL PLAN

11.1 Overall Study Design and Plan

This is a Phase 1, single-site, open label, safety and tolerability, PK, and PD trial of S 48168 (ARM210) with approximately 8-20 individuals with *RYR1*-RM completing the study. Participants will be dosed for approximately 28 days (not to exceed 30 days) at 120 mg or 200 mg daily of S 48168 (ARM210). To date, three participants have been dose at 120 mg and three have been dosed at 200 mg. This study is being conducted in the US at the National Institutes of Health (NIH) in the Neurogenetics Branch of NINDS in collaboration with ARMGO Pharma Inc (the Sponsor), and Les Laboratoires Servier.

The overall design of the study is shown below (Figure1)

[figure not shown]

Figure 1: Study Design

For each participant, the study duration will be approximately 2 months from enrollment to completion. Overall there will be three visits at the NIH CC, Bethesda, MD; one prior to the first dose, one at the end of the dosing period, and one approximately 2 weeks after cessation of S 48168 (ARM210). The last visit will include a blood draw for safety labs, and the full battery of exploratory efficacy assessments. Study participants are contacted by telephone/secured email approximately weekly for a follow-up regarding AEs and can also describe daily any symptoms in a subject diary. Follow-ups will serve to encourage study compliance. The dosing interval for S 48168 (ARM210) will be approximately 28 days (not to exceed 30 days). A study investigator will contact participants by telephone to remind them of upcoming, scheduled local phlebotomy appointments if relevant.

Safety will be monitored throughout the study by repeated clinical and laboratory evaluations.

Discontinued subjects may be replaced at the discretion of the Sponsor in consultation with the PI and DSMB. The pre-screening accrual ceiling will be up to 50 subjects with a target number of approximately 8-20 completers.

Overview of study visits:

Pre-screening of individuals will be conducted by the study coordinator who will use prior medical records and biospecimen data and/or an IRB-approved script (Appendix # 2). During pre-screening, interested individuals may be asked pre-specified questions pertaining to the inclusion and exclusion criteria if needed.

Informed consent will be obtained before any study procedures begin, including formal screening procedures. Formal screening will initiate remotely, upon completion of a telephone consent form for a blood draw. Remote analysis of CYP2C8 genotype will be done at this initial stage of consent to avoid unnecessary burden for the participants who do not meet this inclusion criterion.

The first study visit will begin with the completion of an in-person consent form, covering screening procedures to be conducted at the NIH Clinical Center (e.g. PE, safety laboratory assessments, PFT, ECG) and all remaining study procedures. Participants that complete the study screening assessments at NIH and meet all the eligibility criteria (per an IRB-approved eligibility checklist, Appendix # 3) will receive an allocation number. This number will be distinct from the participant's baseline number. Next, participants will undergo muscle/motor function assessments. They will fast overnight. The following morning, administration of the first dose will begin and participants will remain at the NIH CC for at least 24 hours for single-dose PK (baseline 24hr PK for drug naïve participants only), safety labs, ECG, vital signs and physical examination. Participants will then be discharged, provided with a lifestyle recommendations sheet (Appendix # 4) and contacted approximately one week later for AE assessment (Appendix # 5) by a study investigator (Day 7 ± 2 days). Re-enrolled participants will be assigned a new allocation number. Re-enrolled participants will not undergo baseline 24hr PK studies and will be discharged and instructed to take the study drug after all baseline safety assessments (safety labs, ECG, vital signs and physical examination) are completed.

Participants will attend a phone call on Day 14 (± 2 days). This will include review of any concomitant medication, TEAE assessment, and C-SSRS and PROMIS-fatigue questionnaires. Safety labs will be obtained remotely or at NIH CC if the participant is local to the study site.

Participants will return to the NIH CC on Day 28 (± 2 day) for repeat safety labs, ECG, vital signs, physical examination, and 24hr PK. In addition, participants will be observed and examined one day post cessation of dosing, for any withdrawal effects, although none are expected.

A study investigator will contact participants by telephone weekly when not on site to remind them of upcoming, scheduled local phlebotomy appointments and perform remote TEAE assessments, if applicable.

The final onsite study visit (Day 42 ± 2 Days) will consist of muscle/motor function assessments, PROMIS-fatigue questionnaire, AE assessment, vital signs, physical examination, safety labs, and a blood draw.

Daily subject diaries will be used to capture both time of dose administered as well as any symptoms they may feel in between remote TEAE assessments.

Confinement, Return Visits, and Follow-Up

Participants will be admitted to the NIH CC on the evening of Day -1 for drug administration. Drug naïve participants will undergo baseline 24hr PK sample collection the next morning.

Participants will attend a phone call on Day 14 (± 2 days). This will include review of any concomitant medication, TEAE assessment, and C-SSRS and PROMIS-fatigue questionnaires. Safety labs will be obtained remotely or at NIH CC if the participant is local to the study site.

Participants will return to the NIH CC on Day 28 (± 1 day) for repeat safety labs, PE, ECG, vital signs, and a 24hr PK sample collection.

Participants will return to the NIH CC for Day 42 ± 2 days for vital signs, AE assessment, exploratory efficacy assessments, safety labs, and a blood draw.

At all times, a subject may be required to remain at the NIH CC for longer at the discretion of the Principal Investigator (PI) or designee (e.g. when deemed necessary for safety reasons).

Participants will be contacted by telephone/secured email for a follow up regarding TEAEs approximately weekly when not on site and will also have a blood draw for safety clinical laboratory tests at day 14. This will include participants who terminate the study early. Participants local to the study site will have the option of completing AE assessments and safety clinical laboratory tests at the NIH.

Participants will also be able to enter any symptoms they experience in a participant diary (Appendix # 6).

11.2 Risks and Discomforts

Medical History

There may be some psychological distress associated with providing medical and family history. Frequent breaks may be taken to decrease the risk of distress.

Suicidality assessment

There may be some psychological distress associated with completing the suicidality assessment. Frequent breaks may be taken to decrease the risk of distress. There is a risk that

the suicidality assessment will be positive. If positive, we will take steps to assure the participant's safety and well-being.

Physical Examination

There is minimal medical risk and discomfort from the physical examination.

Videotaping

Risks are minimal. The patient may be identified if a face is featured. When possible, the patient's face and other identifying marks will not be included in the recording or photograph in order to protect confidentiality.

Pulmonary Function Tests

There are minimal risks. Participants may feel tired after the procedures.

Cardiac assessment (ECG and Echocardiogram)

Patients may experience slight discomfort from laying still. These are minimal risk procedures however patients may experience discomfort with removal of the electrodes or a topical reaction to the adhesive on the electrodes.

Cannulation and phlebotomy

Participants may have some discomfort and bruising at the site of cannulation/needle entry. There is a minimal risk of fainting. Infection in the area of the cannulation/needle insertion is rare. To address this risk cannulation and phlebotomy will be conducted by clinicians / phlebotomists.

Pregnancy testing

There is a risk that a pregnancy test will be positive. This may be upsetting to the participant. A clinician will be present the results to the participant and be available for any questions.

Urine collection

There is minimal risk associated with urine collection.

Motor Function Measure 32

Participant self-limiting tests with minimal risk and discomfort. Participants may become fatigued.

Graded Functional Tests

These are patient self-limiting tests with minimal risk and discomfort. Participants may become fatigued.

Grip/Pinch Strength: These are patient self-limiting tests with minimal risk and discomfort. Participants may become fatigued.

Quantitative Muscle Assessment: Participant self-limiting test with minimal risk and discomfort. Participants may become fatigued.

PROMIS-fatigue:

This is a minimal risk procedure.

Remote TEAE reporting

There may be some psychological distress associated with recalling adverse events. A clinician will conduct remote TEAE reporting data collection and be available for any questions the participant may have relating to their responses. Participants local to the study site will have the option of completing TEAE assessments at the NIH.

Post-study follow-up blood draw

The risks associated with phlebotomy (detailed above) apply. A study investigator will contact participants by telephone to remind them of upcoming, scheduled local phlebotomy appointments.

Administration of study drug

As this is a phase 1 study, and the first time S 48168 will be administered to a patient population, we consider administration of study drug to be greater than minimal risk. To date however, data are available for a total of 107 adult healthy male Caucasian participants aged 18-45 years that participated in Phase 1 clinical studies. Of these participants, 90 were exposed to S 48168 (ARM210) treatment. S 48168 (ARM210) has been safe and well-tolerated in single doses up to 240 mg and in 14 days of multiple dosing up to 240 mg daily (un-blind data), and in single dose of 400 mg and 14 days of multiple dosing of 240 mg daily (blinded data). No serious AEs were reported. There were no clinically significant, dose dependent changes in vital signs, physical examination, laboratory data, ECG and telemetric data.

Risk to the participant from study drug administration will be minimized through 24h inpatient monitoring following administration of the first dose and AE monitoring scheduled throughout the intervention phase as well as 1 day, 7 ± 2 days, and 14 ± 2 days post-intervention. As a precaution, all participants will be provided with a malignant hyperthermia alert bracelet and asked to wear this throughout the study and two-week follow-up.

11.3 Human Subjects Protection

11.3.1 Subject Selection

Subject selection will be equitable considering the rarity of *RYR1*-RM. Pediatric *RYR1*-RM affected individuals are not being considered for this trial since clinical trials of S 48168 (ARM210) have only been completed in adult healthy volunteers to date. All ages within the specified range, races, and both sexes will be accepted. Individuals over 65 years of age will be excluded from participation in this study to avoid potential increased risks due to pre-existing conditions or confounding factors (e.g. from concomitant medication use and age-related muscle weakness (sarcopenia)).

11.3.2 Justification for Exclusion of Children

Children (individuals below 18 years of age) will be excluded from participating in this trial since clinical trials of S 48168 (ARM210) have only been completed in adult healthy volunteers to date.

11.3.3 Justification for Exclusion of Other Vulnerable Subjects

Those unable to provide consent due to cognitive issues will be excluded, due to the requirement to be able to respond to remote TEAE reporting.

11.3.4 Safeguards for Vulnerable Populations and Sensitive Procedures

For women of childbearing age, we will do pregnancy testing to exclude those who are pregnant at the beginning of the study. We will also exclude women who are breastfeeding. Women who are sexually active will require contraception. Acceptable contraception includes hormonal methods (oral contraceptives, the patch, shot/injection, and vaginal ring), implantable devices (implantable rods and intrauterine devices), and permanent birth control methods (sterilization implant and surgical sterilization).

11.4 Anticipated Benefit/Classification of Risk

Anticipated Benefits: This study may offer a temporary direct benefit to participants allocated to receive S 48168 (ARM210), such as improved skeletal muscle function owing to enhanced RyR1-Calstabin1 binding and, in turn, improved excitation-contraction coupling. The short nature of this study may limit these benefits.

Overall Risk and Benefit Ratio: The risks are reasonable in relation to the anticipated benefit in this adult patient population.

11.5 Alternative to Participation

As this study is a clinical trial to determine the effects of S 48168 (ARM210) on patients with *RYR1*-RM, it is necessary for participants in the trial to take S 48168 (ARM210). S 48168 (ARM210) is used under an IND. For patients who do not wish to take S 48168 (ARM210) the alternative is to not participate in the trial. There are no approved therapeutic alternatives.

11.6 Selection of Study Population

11.6.1 Inclusion Criteria

Patients must meet all the following conditions to be eligible for enrollment into the study:

1. Adult males and females, 18 – 65 years of age, inclusive, at screening.
2. Body mass index (BMI) ≥ 18.0 and $\leq 36.0 \text{ kg/m}^2$ at screening.

3. Confirmed genetic diagnosis of *RYR1*-RM and supporting clinical phenotype with demonstrable deficits on at least one of the baseline study assessments.
4. Evidence of functional deficit (defined by MFM-32 \leq 80% maximum score) or demonstrable deficits in at least one of the baseline muscle/motor function assessments.
5. Ambulatory. Able to walk ten meters (with or without assistance e.g. with a cane).
6. Must have a CYP2C8 extensive or intermediate metabolizer genotype.
7. Daily use of medicines and dietary supplements need to be approved by the PI and Sponsor, or a drug/supplement-dependent wash-out prior to inclusion.
8. For male subjects: is sterile or agrees to use an appropriate method of contraception, including a condom with spermicide, from study drug administration on the first day of dosing until 5 half-lives plus 90 days (approximately 94 days) after the last dose of study drug administration. No restrictions are required for a vasectomized male subject provided the subject is at least 1-year post-bilateral vasectomy procedure prior to study drug administration on first day of the first dose. A male subject whose vasectomy procedure was performed less than 1 year prior to study drug administration on the first day of dosing must follow the same restrictions as a non-vasectomized male. Appropriate documentation of surgical procedure should be provided.
9. For male subjects: agrees to not donate sperm from study drug administration on the first day of dosing until 5 half-lives plus 90 days (approximately 94 days) after the last dose of study drug.
10. For female subjects of childbearing potential: uses one of the following highly effective birth control methods (from the first dose until 5 half-lives plus 90 days (approximately 94 days)):
 - Prescribed hormonal oral contraceptives, vaginal ring, or transdermal patch.
 - Intrauterine device (IUD).
 - Intrauterine hormone-releasing system (IUS).
 - Depot/implantable hormone (e.g., Depo-provera®, Implanon).
 - Bilateral tubal occlusion/ligation.
 - Sexual abstinence:
 - Refraining from heterosexual intercourse during the entire period of risk associated with the study requirements.
 - If the participant decides to become sexually active during the study, then one of the highly effective birth control methods must be used.
11. For female subjects of non-childbearing potential; defined by at least 1 of the following criteria:

- Postmenopausal defined as 12 months of spontaneous amenorrhea and follicle-stimulating hormone (FSH) serum level > 40mIU/mL. Appropriated documentation of FSH levels is required.
- Surgically sterile by hysterectomy and/or bilateral oophorectomy with appropriate documentation of surgical procedure.
- Has a congenital condition resulting in no uterus.

12. Willingness and ability to comply with scheduled visits, drug administration plan, laboratory tests, study restrictions, and study procedures

13. Able to provide written informed consent and understands the study procedures in the informed consent form (ICF).

11.6.2 Exclusion Criteria

The presence of any of the following conditions will exclude a patient from study enrollment:

1. Patient is mentally or legally incapacitated at the time of the screening visit or during the conduct of the study.
2. History or presence of alcoholism or drug abuse within the past 2 years prior to the first dose of study drug.
3. History or presence of hypersensitivity or idiosyncratic reaction to the study drug, related compounds, or inactive ingredients.
4. Positive urine drug or alcohol results at screening.
5. Positive results at screening for human immunodeficiency virus (HIV), hepatitis B surface antigen (HBsAg), or hepatitis C virus (HCV).
6. Patients with baseline ALT levels three times above the upper limits of normal (ULN) or baseline AST levels five times the ULN (isolated elevations of total bilirubin <2 X ULN with direct bilirubin below the ULN will be included).
7. Patients with severe pulmonary dysfunction at screening (Forced Vital Capacity (FVC) < 50% predicted) or evidence of pulmonary exacerbation. Pulmonary exacerbations refer to an acute worsening of respiratory symptoms that result from a decline in lung function.
8. Patients with a history of a seizure.
9. Subject has a history of cancer (malignancy) Exceptions: (1) Subjects with adequately treated non-melanomatous carcinoma or carcinoma in situ of the cervix may participate in the trial (2) Subjects with other malignancies who have been successfully treated > 10 years prior to the screening where in the judgment of the investigator has revealed no evidence of recurrence from the time of treatment through the time of the screening except those identified at the beginning of the exclusion criterion or (3) Subjects who in the

opinion of the investigator are highly unlikely to sustain a recurrence for the duration of the trial.

10. Patients with uncontrolled diabetes defined as HbA1c > 7% or diabetic neuropathy.
11. Estimated creatinine clearance <40 mL/minute at screening, which may be calculated using the Chronic Kidney Disease Epidemiology Collaborative method (CKD-EPI), due to reduced muscle mass often seen in *RYR1*-RM patients.
12. Patients with a clinically significant abnormality on their ECG other than hypertensive related, or heart failure (ejection fraction <30%) or other clinically significant structural heart disease on echocardiogram.
13. Patients with a history of myocardial infarction in the last five years, or evidence of congestive heart failure.
14. Pregnant and breastfeeding women.
15. Unable to refrain from or anticipates the use of:
 - Any non-approved medicines and/or dietary supplements beginning 14 days prior to the first dose of study drug and throughout the study. Thyroid hormone replacement medication may be permitted if subject has been on same stable dose for the last 3 months prior to the first dose of study drug.
 - Any drugs known to be significant inducers or inhibitors of CYP2C8 enzymes for 28 days prior to the first dose of study drug and throughout the study. Any substrates of breast cancer resistance protein (BCRP).
16. Is currently taking any drug which raises gastric pH, including proton pump inhibitors or H2 antagonists. Antacids may be used if taken at night.
17. Donation of blood or significant blood loss within 56 days prior to the first dose of study drug.
18. Plasma donation within 7 days prior to the first dose of study drug.
19. Participation in clinical trials for other therapeutic investigational drugs simultaneously or within the 4 weeks prior to the first dose of study drug.
20. Ongoing medical condition that is deemed by the Principal Investigator to interfere with the conduct or assessments of the study or safety of the subject.
21. Is an NIH employee who is a subordinate/relative/coworker of a study investigator.

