12.10.6 Clinical Laboratory Tests

All tests listed below will be performed as per Study Events Flow Chart ([Section 7](#)). In addition, laboratory safety tests may be performed at various unscheduled time points, if deemed necessary by the PI or designee.

Hematology

- Hemoglobin
- Hematocrit
- Total and differential leukocyte count
- Red blood cell count
- Platelet count
- HbA1C (screening only)

Serum Chemistry*

- Blood Urea Nitrogen
- Bilirubin (total and direct)
- Alkaline phosphatase
- Aspartate aminotransferase
- Alanine aminotransferase
- Gamma-glutamyl transferase
- Creatine Kinase
- Albumin
- Sodium
- Potassium
- Chloride
- Glucose (fasting)
- Creatinine**
- Cystatin C

Urinalysis

- pH
- Specific gravity
- Protein***
- Glucose
- Ketones
- Bilirubin
- Blood***
- Nitrite***
- Urobilinogen
- Leukocyte esterase***

Additional Tests

- HIV test
- HBsAg
- HCV
- Urine drug screen
 - Opiates
 - Amphetamines
 - Cocaine
 - Cannabinoids
- Urine alcohol screen
- Serum pregnancy test****
(for females only)
- FSH (for postmenopausal females at screening only)

* Serum chemistry tests will be performed after at least an 8-hour fast; however, in case of dropouts or rechecks, subjects may not have fasted for 8 hours before the serum chemistry sample is taken. Participants will be encouraged to drink water as usual during the fast.

** At screening, creatinine clearance will be calculated using the CKD-EPI formula.

*** If urinalysis is positive for protein, blood, nitrite and/or leukocyte esterase, a microscopic examination (for red blood cells, white blood cells, bacteria, casts, and epithelial cells) will be performed.

**** Pregnancy tests must be confirmed as negative prior to administering the first dose. Contraception will be required for women of childbearing potential who are sexually active. If a pregnancy test is positive, the study participant will be notified of the results. Women who become pregnant during the study will be withdrawn and followed through their pregnancy and birth.

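### The renal exclusion gives low muscle mass as its reason for CKD-EPI, yet its footnote ties the calculation to creatinine, which makes the estimate read high when muscle mass is low

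*Protocol*

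**What the plan says.** Criterion 11 in Protocol 11.6.2 excludes "Estimated creatinine clearance <40 mL/minute at screening". It allows CKD-EPI for the calculation and gives its reason, describing the value as one "which may be calculated using the Chronic Kidney Disease Epidemiology Collaborative method (CKD-EPI), due to reduced muscle mass often seen in" this population.

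Protocol 12.10.6 lists the serum chemistry tests. Creatinine is the only one carrying the double-asterisk footnote, which reads: "At screening, creatinine clearance will be calculated using the CKD-EPI formula". Cystatin C is on the same list with no footnote. The section adds: "All tests listed below will be performed as per Study Events Flow Chart", and the flow chart in Protocol Section 7 marks serum chemistry at screening. Cystatin C is therefore available when eligibility is decided.

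Neither document names the CKD-EPI equation. SAP 8.3 summarises and lists laboratory values but gives cystatin C no part in any renal estimate.

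**The concern.** The criterion recognises that muscle mass is a problem for estimating renal function in these patients. The footnote then points to the marker that muscle mass affects. Creatinine comes from muscle: with less muscle, serum creatinine is lower at the same true clearance, and an estimate built on it is higher. Changing the formula does not remove this if the input is still creatinine. The stated reason argues against the method as written.

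For an exclusion rule, an upward error is the permissive direction. Someone the protocol means to exclude could be admitted to a Phase 1 study whose primary objective is safety and tolerability.

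The point still affects entry. Six participants have been dosed against a target of about 8-20 completers (Protocol 11.1), and low-dose participants who re-enrol must meet all criteria again (Protocol 12.2).

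**Working it through.** The 40 mL/min limit is a fixed threshold, not a derived figure, so there is no calculation in the plan to reproduce. The check has two parts.

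**1. The text, side by side**

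| Item | Protocol 11.6.2, criterion 11 | Protocol 12.10.6 |
|---|---|---|
| Quantity | Estimated creatinine clearance | Creatinine clearance |
| Method | CKD-EPI, permissive (*may*) | CKD-EPI, mandatory (*will*) |
| Marker | Not named beyond the quantity itself | Footnote sits on creatinine |
| Reason | Reduced muscle mass | None given |
| Cystatin C | Not mentioned | Measured, no footnote, no stated use |

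Taken literally, "creatinine clearance will be calculated using the CKD-EPI formula" with creatinine as the input.

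**2. Direction and size**

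Input from the documents: the limit of 40 mL/min.

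Assumptions, neither of them in the documents:
- Serum creatinine is lower by a fraction r, solely because less is produced, with r from 0.10 to 0.40.
- The estimate varies as creatinine to the power -k, with k from 1.0 to 1.2.

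Then:
- reading = true value x (1 - r)^(-k)
- true value when the reading is 40 = 40 x (1 - r)^k

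For example, with r = 0.20 and k = 1.0, a reading of 40 means a true value of 40 x 0.80 = 32.0. With r = 0.40 and k = 1.2 it means 40 x 0.60^1.2 = 21.7.

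| Creatinine lower by | True value when the reading is 40 (k = 1.0 to 1.2) | Reading when the true value is 35 (k = 1.0 to 1.2) |
|---|---|---|
| 10% | 36.0 to 35.2 | 38.9 to 39.7 (still excluded) |
| 20% | 32.0 to 30.6 | 43.8 to 45.7 (passes) |
| 30% | 28.0 to 26.1 | 50.0 to 53.7 (passes) |
| 40% | 24.0 to 21.7 | 58.3 to 64.6 (passes) |

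The error is upward in every row. Its size depends on r, for which the documents offer no value.

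**The case against.** The strongest reply is that the equation is not named. The criterion gives muscle mass as its reason and cystatin C is in the panel, so a cystatin C equation may have been intended and loosely worded. That is possible, and the documents do not settle it. It does not remove the point: if that was the intention, the footnote is on the wrong analyte and the same edit is needed.

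A reader might go further than the documents allow in four ways.

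- *That people below the limit would be enrolled and dosed.* Only *could* is supported. Nothing shows how many candidates are near 40. Entrants are 18-65 and ambulatory, with uncontrolled diabetes, congestive heart failure and FVC below 50% predicted excluded. At a 10% creatinine deficit, a true value of 35 is still screened out.
- *That renal harm would follow.* No section describes renal elimination or renal toxicity. Protocol 9.4 describes CYP2C8 as a main metabolic pathway and lists CNS, testicular and gastric findings. None of the adverse events of special interest is renal.
- *That cystatin C is wholly unused.* As a chemistry test it falls under the SAP's listings and summaries, and criterion 20 leaves the investigator discretion. What is missing is a stated role in criterion 11.
- *That a units mismatch makes the rule more lenient still.* The documents do not say whether the CKD-EPI result is indexed to body surface area. If it were per 1.73 m², the effect would go both ways: a reading of 40 would be 40 x 1.4/1.73 = 32.4 mL/min at 1.4 m², but 40 x 2.0/1.73 = 46.2 mL/min at 2.0 m². This supports asking for the units to be stated. It supports neither a one-sided magnitude nor a compulsory conversion.

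**Conclusion.** The concern stands as an internal mismatch with a known direction and an unknown size. As written, criterion 11 and its footnote rest on a marker that the criterion's own reason makes unreliable. The resulting error favours admission, and cystatin C, measured at screening, has no role in the decision.

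Under the assumed 10-40% deficit and exponent of 1.0-1.2, the nominal limit of 40 acts as a true limit of about 36 down to 22 mL/min. These figures are illustrative. The direction rests only on lower creatinine production with less muscle; the size rests entirely on the assumed ranges. This should be corrected, but the documents do not show that any participant has been or will be wrongly admitted. No view is taken on whether 40 is the right limit.

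**What to change.** In criterion 11 and the double-asterisk footnote of Protocol 12.10.6:

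- Take the screening value for criterion 11 from the cystatin C already measured, using a named CKD-EPI equation that uses cystatin C, and move the footnote to that analyte.
- Reconcile *may* with *will*, so that both sections give one method.
- State the units in which the result is compared with the limit.
- Leave the limit of 40 unchanged.

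The cost is amendment wording and an edit to the eligibility checklist, with no new sample or visit. An occasional candidate who passes on creatinine would be screened out, which matters somewhat in a rare disease. Cystatin C also has non-renal influences of its own, so it is not free of error. It does address the muscle-mass problem that the protocol itself names.
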